6.4.2. Listings

Data listings will be sorted by treatment group (for unblinded analysis), subject number, and cycle number, if applicable.

6.4.3. Dates

Dates will be displayed in ddmmmyyyy format (e.g., 30JUN2002).

Calculations using dates will adhere to the following conventions:

- Study days after the start day of study drug will be calculated as the difference between the date of interest and the first date of dosing of study medication (e.g, lenalidomide) plus 1 day. The generalized calculation algorithm for relative day: $STUDY\ DAY = [(TARGET\ DATE - DSTART) + 1]$ where DSTART = the start day of study drug]. Note that Study Day 1 is the first day of treatment of study drug. For study days before the start day of study drug the algorithm is: $STUDY\ DAY = (TARGET\ DATE - DSTART)$. Negative study days are reflective of observations obtained during the baseline/screening period.
- Age (expressed in days) is calculated: $AGE = Date\ of\ randomization - DTBIRTH + 1$. In practice, age will be converted to years by dividing the difference by 365.25 days, then truncating to a whole number.
- The conversion between weeks and months can be performed by using the following conversion formula (without truncation):
 $MONTHS = WEEKS * 7/30.4$.
- Partial dates will be reported as recorded in the data listings. There will be no imputation for missing parts of dates, unless for the purpose of
 1. determining treatment emergent AEs when the AE start date is partial, or
 2. differentiating medication taken prior to the study treatment from concomitant medication taken during the study when the medication start date is partial.

The conventions for imputing partial dates for such purposes are as follows:

1. The onset date has year but both month and day missing
 - If the year of onset = year of first study drug dose, then the onset date = First study drug dose date.
 - If the year of onset < year of first study drug dose, then the onset month = 12 and the onset day=last day of the month.
 - If the year of onset > year of first study drug dose, then the onset month = 1 and the onset day=1.
2. The onset date has year and month but day missing
 - If the year and month of onset = year and month of first study drug dose, then the onset date = first study drug dose date.

- If the year of onset $<$ year of first study drug dose, or the year of onset = year of first study drug dose but the month of onset $<$ the month of first study drug dose, then the onset day = last day of the month.
- If the year of onset $>$ year of first study drug dose, or the year of onset = year of first study drug dose but the month of onset $>$ month of first study drug dose, then the onset day = first day of the month.

7. SUBJECT DISPOSITION

For all subjects randomized, subject disposition will be summarized. Subject disposition includes the number of subjects in the following categories:

- ITT Population
- Safety Population

Reasons for treatment termination will be collected on the CRF and will be summarized for all randomized subjects with the following categories:

- AEs that, in the judgment of the Investigator, may cause severe or permanent harm or which rule out continuation of study drug.
- Disease progression with or without histologic transformation
- Subject withdraws consent
- Subject lost to follow-up
- Death
- Protocol violation

A separate listing will be provided for subjects not treated.

8. DEMOGRAPHICS AND BASELINE CHARACTERISTICS

Subjects' age, weight, and other continuous demographic and baseline variables including disease characteristics will be summarized using descriptive statistics (e.g., mean, standard deviation, median, minimum and maximum), while the response to previous CLL treatment, race and other categorical variables will be summarized with frequency tabulations for each treatment arm separately and pooled over all treatment arms. Cytogenetic abnormalities will be identified and summarized by treatment arm.

Homogeneity of these variables will be assessed by t-test for continuous measures and by Fisher's exact test for categorical measures. If any significant differences ($p < 0.10$) are found between treatment arms, additional exploratory analyses will be performed to assess the impact of this lack of baseline homogeneity on relative treatment effects.

Summaries for the demographics and baseline characteristics will be provided for the ITT population and safety population separately. Individual subject listings will be provided.

Medical history data will be summarized using frequency tabulations for each treatment arm by system organ class and preferred term separately and pooled over all arms using the safety population.

9. DRUG EXPOSURE

The following measures of drug exposure will be analyzed for lenalidomide and placebo.

Treatment Duration

The first dose date of lenalidomide or placebo is considered the start date of the overall study treatment. For each cycle, the lenalidomide/placebo start date will be considered the cycle start date and the day before that (after the 1st cycle) will be considered the end day of the previous cycle. The end date of the last cycle will be calculated as the start date of last treatment cycle plus 27 days, unless subject discontinues study or dies before the end of the last cycle, in which case the end date of the last cycle will be the treatment discontinuation date or the death date. The overall study treatment end date will be the same as the end date of the last cycle of the last study drug. The overall treatment duration (days) is defined as:

$$[(\text{The overall study treatment end date}) - (\text{the first study drug start date}) + 1]$$

For each study drug (i.e., lenalidomide or placebo), the treatment duration will also be calculated, and defined as:

$$[(\text{The end of the last cycle of the study drug}) - (\text{the first dose date of the study drug}) + 1]$$

Cumulative Dose

Cumulative dose will be calculated for lenalidomide arm. The cumulative dose is defined as the sum of all doses taken across the treatment period (in milligrams).

Dose Exposure

Dose exposure will be calculated for lenalidomide arm. Dose exposure is defined as the number of days on the study drug during the treatment phase (excluding the periods of dose interruptions).

Average Daily Dose

Average dose will be calculated for lenalidomide arm. Average daily dose is defined as the cumulative dose divided by dose exposure (mg/day).

Dose Intensity

Dose intensity will be calculated for lenalidomide arm. Dose intensity is defined as the cumulative dose divided by treatment duration (mg/day).

Descriptive statistics of treatment duration, cumulative dose, dose exposure, average daily dose, and dose intensity, will be presented by treatment arm. In addition, descriptive statistics for treatment duration in weeks and associated frequency tables, as well as the number of cycles on study drug, will be presented by treatment arm, for both induction therapy period and the whole double-blind treatment period.

The dosing statistics as described above may be presented by cycle.

Dose reduction/interruption and re-escalation will be summarized. Summaries will include subjects who have at least one dose reduction/interruption due to AE, time to first dose reduction/interruption due to AE. Additional descriptive statistics will include, subjects who have a second dose reduction/interruption due to AE, duration of first and second dose

reduction/interruption due to AE and interval between first and second dose
reduction/interruption due to AE.

Number of subjects who reached 5 mg at Cycle 2 and 10 mg at Cycle 7 will also be summarized.

As an exploratory analysis, the dosing statistics above might be summarized by treatment arm and study drug for different age groups (≤ 70 yrs and > 70 yrs) to examine the possible difference in dosing tolerability by age.

[REDACTED]

11. EFFICACY ANALYSIS

Efficacy analyses will be performed on the intent-to-treat (ITT) population that includes all subjects randomized. Primary analyses will be performed in two steps with a Bonferroni adjustment used to control the error rate.

The first step is to compare PFS after at least 160 subjects across both treatment arms have progressed or died. An interim analysis for OS will also be performed at this time. If the PFS difference between the two treatment groups is significant and OS results do not show a negative effect for the lenalidomide treatment group, then lenalidomide treatment will be deemed efficacious. Furthermore, if the OS interim reaches the pre-specified O'Brien-Fleming boundaries and PFS is not statistically significant but not negative for lenalidomide, then lenalidomide will be deemed efficacious. These analyses will be performed by an independent statistician not associated with the trial. The results will be shared only with the DMC who will decide the future course of the study. Specifically, if either (or both) of the two efficacy conditions described above are met, then the DMC could recommend that the blind be broken and analyses be performed by the sponsor.

The second step will be the comparison of OS. This analysis will be performed when at least 160 subjects across both treatment arms have died. This analysis will be performed regardless of the outcome of the analysis of PFS. If no significant differences in PFS are found during the first step analysis, but differences are found in OS during the second step in favor of lenalidomide treatment group, the treatment will be deemed efficacious. Exploratory analysis on PFS will also be performed at this time.

Secondary analyses will be performed to characterize change in tumor response, duration of improved response, HRQL, and PFS2. If either of the co-primary endpoints is significant, a fixed sequence testing procedure will be used for the secondary endpoints with the following order: tumor response, duration of response. The Kaplan-Meier procedure will be used to characterize the time-to-event curves in these analyses when there is censoring. Stratified log ranks tests will be used to compare the time-to-event curves. Analysis of variance/covariance (ANOVA/ANCOVA) will be used to compare HRQL and EQ-5D total scores and subscores across the two treatment arms. Otherwise, summary statistics (mean, standard deviation, median, minimum and maximum) and relevant confidence intervals will be provided.

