**Study Design:**

CC-5013-CLL-002 is a phase 3, multicenter, randomized, placebo-controlled, parallel-group study that will compare the efficacy and safety of oral lenalidomide maintenance therapy to that of placebo in patients with B-cell CLL who achieved at least partial response (PR) with second-line therapy. The primary efficacy objective of this study is to demonstrate superiority of lenalidomide over placebo in prolonging overall survival (OS) due to continued therapy, for all subjects, including subjects with or without poor prognostic factors, subjects of various ages and subjects with PR, nodular partial response (nPR), complete response with incomplete bone marrow recovery (CRi), complete response (CR) and minimal residual disease (MRD)-negative CR. All subjects randomized to the lenalidomide treatment arm, including those subjects who do not improve their response (PR, nPR, CRi or CR) and subjects who do not have the opportunity to improve their response further (MRD-negative CR) will be treated up to disease progression, with the objective to demonstrate prolongation of OS.

Eligible subjects must have been treated with a purine analog-, a bendamustine-, an anti-CD20-antibody-, or a chlorambucil-based regimen in first and/or second line and must have achieved at least PR to second-line induction therapy of sufficient duration. Alemtuzumab-containing regimens will also be allowed for those subjects with 17p deletion. Subjects who achieve stable disease (SD) only or who develop progressive disease (PD) at any time during induction therapy will not be eligible for participation in this study.

Approximately, three hundred twenty (320) subjects with PR, nPR, CRi, CR or MRD-negative CR will be enrolled and randomized (1:1) into two arms: placebo daily or lenalidomide 2.5 mg daily on days 1-28 of the first 28-day cycle. If the 2.5 mg dose level is well tolerated, escalation to 5 mg daily on days 1-28 of each 28-day cycle is permitted starting with the second cycle; for those subjects who tolerate well the 5 mg dose, escalation to 10 mg daily on days 1-28 of each 28-day cycle after 5 continuous cycles at 5 mg will be permitted.

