## 8. INVESTIGATIONAL PLAN

### 8.1. Overall Study Design

CC-5013-CLL-002 is a phase 3, multicenter, randomized, placebo-controlled, parallel-group study that will compare the efficacy and safety of oral lenalidomide maintenance therapy to that of placebo in subjects with B-cell CLL who achieved at least partial response (PR) with second-line therapy. The primary efficacy objective of this study is to demonstrate superiority of lenalidomide over placebo in prolonging OS due to continued therapy, for all subjects, including subjects with or without poor prognostic factors, subjects of various ages and subjects with PR, nodular partial response (nPR), complete response with incomplete bone marrow recovery (CRi), complete response (CR), and minimal residual disease (MRD)-negative CR. All subjects randomized to the lenalidomide arm, including those subjects who do not improve their response (PR, nPR, CRi, or CR) and subjects who do not have the opportunity to improve their response further (MRD-negative CR) will be treated up to disease progression with the objective to demonstrate prolongation of OS.

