## 16. STATISTICAL ANALYSES

### 16.1. Statistical Overview

The objective of the statistical analysis will be to compare the efficacy and safety of lenalidomide versus placebo as maintenance therapy in subjects with relapsed or refractory B-cell chronic lymphocytic leukemia (CLL) having achieved PR or better after second-line therapy.

Overall survival (OS) will be the primary endpoint for the protocol following amendment #10. This analysis will be performed at the completion of the study. It is estimated that at least 160 subjects across both treatment arms have died at the time of analysis (yielding 80% power to detect a 61.3% improvement in median OS for a two-sided test at 0.025 level allowing for one interim analysis).

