5.2. Study Endpoints

For all the efficacy endpoints, the determination of responses (including progression of disease) is based on the central adjudication committee (CAC) review of the CLL response data using IWCLL guidelines for the diagnosis and treatment of chronic lymphocytic leukemia [Appendix 22.4 of the protocol]

Co-primary Endpoints

- Progression-Free Survival (calculated as the time from randomization to the first documented progression confirmed by a blinded, independent Response Adjudication Committee or death due to any cause during or after the treatment period, whichever occurs first)
- Overall Survival (calculated as the time from randomization to death from any cause).

Secondary Endpoints

- Safety [type, frequency, and severity of adverse events (AEs) and relationship of AEs to lenalidomide]
- Tumor Response, including evaluation of minimal residual disease (MRD) by flow cytometry (improvement of the quality of response)
- Duration of response
- Health-Related Quality of Life (HRQL) by Functional Assessment of Cancer Therapy-Leukemia (FACT-Leu) and EQ-5D

- Progression Free Survival 2 (PFS2)

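### SAP 11 can deem lenalidomide efficacious on significant PFS with OS merely not negative, whereas the protocol after Amendment 10 has OS as its only primary endpoint

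*SAP*

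**What the plan says.** **SAP.** Section 5.2 lists PFS and OS under "Co-primary Endpoints", the first being "Progression-Free Survival (calculated as the time from randomization to the first documented progression confirmed by a blinded, independent Response Adjudication Committee" or death. Each is tested at two-sided 0.025 (11.1.1, 11.1.2), a Bonferroni split. Section 11 gives three routes to success:

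- Step 1, at about 160 PFS events: "If the PFS difference between the two treatment groups is significant and OS results do not show a negative effect", "then lenalidomide treatment will be deemed efficacious".
- Step 1: OS crosses its interim boundary and PFS, though not significant, is not negative.
- Step 2, at 160 deaths: PFS was not significant at step 1, but OS is now significant in favour of lenalidomide.

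On the step-2 OS test, Section 11 says "This analysis will be performed regardless of the outcome of the analysis of PFS". The paragraph of Section 11 on secondary analyses opens fixed-sequence testing of tumor response and duration of response once either co-primary endpoint is significant, with no condition on OS.

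**Protocol.** Section 16.1: "Overall survival (OS) will be the primary endpoint for the protocol following amendment #10". Section 7.1 names OS only, and 7.2 names safety and PFS2. Section 8.1 gives the efficacy aim as "to demonstrate superiority of lenalidomide over placebo in prolonging OS due to continued therapy". The synopsis retires the Response Adjudication Committee from Amendment 10. First-progression PFS remains only in the synopsis sizing sentence and in the rule for closing enrolment. A redacted block follows 7.2, so an exploratory role for PFS cannot be excluded.

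**The concern.** The SAP gives one verdict for the whole trial, and one route to it needs no significant OS result. The protocol now defines the trial by OS. If PFS is significant, OS is not negative at about 60% information, and OS then fails at 160 deaths, the readable SAP text leaves the step-1 verdict standing and the protocol's only primary endpoint is missed. Neither document says which governs. At stake is the main conclusion of the study report, in a trial that is now open-label (Protocol 10.3). The secondary-testing gate has the same problem: significant PFS opens confirmatory testing of endpoints that the protocol does not list as secondary.

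**Working it through.** **1. Rules side by side.**

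| PFS at step 1 | OS | SAP 11 | Protocol primary endpoint (inferred) |
|---|---|---|---|
| significant | significant, favours lenalidomide | efficacious | met |
| significant | not significant, not negative at step 1 | efficacious | **not met** |
| significant | negative at step 1, not significant at step 2 | no route to success | not met |
| not significant | not significant | no route to success | not met |

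Only the second row diverges.

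**2. The plan's own figure.** Inputs: HR 0.62, 160 events, 1:1 allocation, two-sided 0.025, stated power 80% (Protocol 16.9, SAP 6.1). With the Schoenfeld approximation, Z has mean √(160/4) × −ln 0.62 = 6.325 × 0.478 = 3.023. Power = Φ(3.023 − 2.241) = Φ(0.782) = 78.3%, within 2 points of the stated 80%. It applies to PFS and to OS alike. With one OS look at 60% information (SAP 14.2) and O'Brien-Fleming-type spending, OS power is 78.1%, with nominal p of about 0.0025 at the interim and 0.0242 at the end. The SAP's own boundary table is redacted, so these two p-values are recomputed.

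**3. What OS needs.** Observed HR at significance with 160 deaths: exp(−2.241/6.325) = 0.70. By contrast, the OS condition in the PFS route may be satisfied by any interim HR below 1.

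**4. How often the second row occurs.** PFS (160 events), interim OS (0.60 × 160 = 96 deaths) and final OS (160 deaths) were simulated as correlated normal statistics with means √(events/4) × −ln HR. The two OS looks correlate at √0.6. Assumptions that the documents do not give: the true hazard ratios; a correlation between PFS and interim OS of 0, 0.3 or 0.6; and two readings of not negative. Reading A is interim OS HR below 1. Reading B is no significant harm at the interim (Z above −1.96). Ranges run over the correlation.

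| True PFS HR | True OS HR | OS test succeeds | Diverge, A | Diverge, B |
|---|---|---|---|---|
| 0.62 | 0.62 | 78% | 12–16% | 12–17% |
| 0.62 | 0.80 | 20% | 52–54% | 59–62% |
| 0.62 | 1.00 | 1.25% | 38–45% | 75–77% |
| 1.00 | 1.00 | 1.2% | 0.6–1.1% | 1.1–1.2% |

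Hand check for the third row, reading A, correlation 0: 0.783 × 0.5 = 0.39, less about 0.01 where OS also succeeds, gives 0.38. Divergence requires a significant PFS test, so in the first three rows it cannot exceed 78.3%.

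**5. Multiplicity.** With no effect on either endpoint, the SAP rule declares success for lenalidomide in 1.8–2.4% of trials, inside the one-directional 2.5% implied by 0.025 + 0.025 two-sided. There is no type I error inflation.

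**The case against.** The strongest reply is that these are two stages and not two competing rules. The protocol makes OS primary only following Amendment 10. The SAP describes a double-blind study with a DMC and blinded adjudication, and it places the schedule of assessments in Table 3 of the protocol, whereas the current protocol has it in Table 2. It was evidently written against another protocol version. PFS was pre-specified with its own alpha, and a significant PFS result at a true HR of 0.62 is a true finding. Withdrawing that route now is itself a change to the success rule after unblinding.

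Most of this stands. It explains the mismatch, it rules out any charge of inflated error, and it is why the PFS result should be kept. It does not remove the conflict: the final OS analysis is still to come under the protocol, this is the SAP supplied for it, and followed as written it can return an overall success that the primary endpoint does not support.

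A reader might also infer more than the text bears:

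- *That PFS alone suffices.* The efficacy sentence also requires OS not to be negative. Only the secondary-testing gate lacks an OS condition.
- *That any non-significant OS result splits the documents.* If PFS also fails, or OS is negative at step 1, they agree.
- *That the SAP forbids the final OS test from revising the step-1 verdict.* It is silent on this.
- *That the protocol declares failure.* It states no success rule, its formal objective (6.1) is only to compare efficacy, and its synopsis still sizes for OS and PFS.

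**Conclusion.** The conflict is real but conditional. It arises when PFS is significant and OS is non-significant without being negative. The SAP then says efficacious, while the protocol's sole primary endpoint is not met, as inferred from 7.1, 8.1 and 16.1.

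Its size depends on assumptions. At the planned PFS effect, the documents diverge in roughly 52–62% of trials at a true OS HR of 0.80 and 38–77% at 1.0. The width of the second range comes mainly from the undefined term, which is a finding in itself. At the planned OS effect the figure is 12–17%, and with no effect on either endpoint about 1%. These are frequencies of disagreement between two rules and not false-positive rates.

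A related inconsistency needs settling at the same time. SAP 6.1 explains the 0.025 by the co-primary endpoints, whereas Protocol 16.1 and 16.9 refer only to one interim analysis. With OS as the single primary endpoint, the protocol gives no reason of its own for 0.025.

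**What to change.** Before the final OS analysis, amend SAP 5.2, 6.1, 11, 11.1 and 14.2 to match the current protocol:

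1. State that the primary objective is met only if OS crosses its boundary in favour of lenalidomide.
2. In the sentence on significant PFS with OS not negative, replace the overall efficacy label with an endpoint-specific claim. The step-1 PFS test, at its pre-specified two-sided 0.025, is reported as the pre-Amendment 10 analysis and supports prolonged PFS only. If an OS condition is kept for that claim, give it a numerical criterion.
3. Revise the secondary-testing gate in Section 11 so that it follows the primary rule and the protocol's list of secondary endpoints.
4. Remove or qualify the co-primary wording in 5.2, 6.1, 11.1 and 14.2.
5. Give one reason for the OS alpha of 0.025, the same in both documents.

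Cost: wording only, with no new data or events. PFS no longer yields an overall success label. The change comes after unblinding and must be documented as such, with alignment to Amendment 10 as its reason. Because it removes a route to success and adds none, it cannot raise the false-positive rate of the overall claim.

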$$H_1: F_P(t) \neq F_A(t) \text{ for all } t$$

where F_P is the survivorship function for placebo and F_A is the survivorship function for lenalidomide.

Median PFS will be estimated using Kaplan-Meier estimates, and the 95% confidence intervals (CI) will be computed using the method of Brookmeyer and Crowley. Hazard ratio will be calculated using Cox model stratified for the 3 strata (i.e., response to second-line induction chemotherapy, age, and presence of at least one prognostic factor) to account for the stratified randomization. The Cox model will also be used to identify prognostic factors.

Cross-tabulations will be provided by treatment group to summarize improvements from the best response during induction therapy.

For the primary analysis, the comparison of PFS between the treatment arms using the stratified log rank test, the overall two-sided significance level is 2.5%.

An unstratified log-rank test will also be performed as a secondary analysis for PFS, in addition to the stratified analysis described above.

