11.1.2. Overall Survival (OS)

Overall survival is calculated as the time from randomization to death from any cause. OS will be censored at the last date that the subject was known to be alive for subjects who were alive at the time of analysis and for subjects who were lost to follow-up before death was documented.

The analysis of OS will include survival information for all randomized subjects. Subjects who discontinued from the treatment phase of the study and who had possibly received other anti-cancer therapies and then subsequently died will be included in the analysis as death. However, sensitivity analyses will be performed in which these subjects will be censored at the date of the first dose date of the anti-cancer therapy.

OS will be compared between treatment arms using the stratified log-rank test at 2-sided 0.025 alpha level. The same methods used for the PFS analysis will be used for the OS analysis.

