11.2. Secondary Endpoints and Analysis

11.2.1. Change in Tumor Response

Tumor response, including PD, will be assessed according to the IWCLL guidelines for the diagnosis and treatment of chronic lymphocytic leukemia (Hallek, 2008). Subjects' tumor response status change based on the best response during the treatment period relative to the response at baseline (i.e., from PR, nPR, CRi, CR, MRD-negative CR to PD, nPR, CRi, CR, MRD-negative CR) will be compared in the two arms using Van Elteren's test at a two-sided 0.05 significance level stratified for the 3 strata used at randomization. Responses from subjects after they received other anti-cancer treatments will not be counted; however, these subjects will be included in the denominator. Cross tabulations will be provided to summarize response frequency change comparing to baseline.

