11.2.2. Duration of Improved Response

For those subjects who show improvement from their best response achieved during induction therapy while on study treatment (e.g. PR to CR or CR to MRD-CR), the duration of the improved response will be summarized. The duration of improved response will be calculated at the time from first improvement to the time of disease progression. Duration of improved response will be censored at the date of last assessment showing no worsening from the improved response. A two-sided unstratified log rank test at 0.05 significance level will be used to test the duration of improved response between the two treatment arms.

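### Secondary endpoints are tested at 0.05 after a single co-primary win that releases only 0.025

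*SAP*

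**What the plan says.** SAP section 11 sets the overall scheme: "Primary analyses will be performed in two steps with a Bonferroni adjustment used to control the error rate". Section 11.1.1 gives the PFS level: "the overall two-sided significance level is 2.5" per cent. Section 11.1.2 gives the OS level: "OS will be compared between treatment arms using the stratified log-rank test at 2-sided 0.025 alpha level". On the OS comparison, section 11 adds: "This analysis will be performed regardless of the outcome of the analysis of PFS".

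The gate to the secondary endpoints is also in section 11: "If either of the co-primary endpoints is significant, a fixed sequence testing procedure will be used for the secondary endpoints with the following order". The first test is of tumor response and the second of duration of response. The levels are in the subsections. Under 11.2.1, response is "compared in the two arms using Van Elteren's test at a two-sided 0.05 significance level". Under 11.2.2, "A two-sided unstratified log rank test at 0.05 significance level will be used to test the duration of improved response".

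No visible text lowers the secondary level when only one co-primary has won, or reserves 0.05 for the case where both have. No visible text fixes the data cut-off for the secondary tests either, although 11.2.1 defines response change as "based on the best response during the treatment period relative to the response at baseline", which can change between the PFS step and the final OS step.

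**The concern.** A Bonferroni split with a gated fixed sequence behind it can protect the secondary claims, but only if the sequence is tested at the level that the gate has released. A PFS win releases 0.025. The OS 0.025 is not released, because OS will be tested anyway and a false OS claim is still possible. Testing response at 0.05 after a PFS win therefore spends 0.025 that is still committed to OS. The same holds with the roles of PFS and OS exchanged.

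At stake are the secondary claims after exactly one win: a response or duration result with p between 0.025 and 0.05 would look protected and would not be.

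**Working it through.** **Inputs.** PFS and OS at two-sided 0.025 each (SAP 11.1.1, 11.1.2). Response and duration at two-sided 0.05 (11.2.1, 11.2.2). About 160 events, hazard ratio 0.62, 80% power (SAP 6.1). One OS interim at about 60% information, at the time of the PFS analysis (SAP 14.2). The documents give no correlations between endpoints.

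**The plan's power figure.** √160/2 × |ln 0.62| − 2.241 = 3.023 − 2.241 = 0.782, which gives 78.3% power. This agrees with the stated 80% to within 2 points, so I use 80%.

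**Setting.** PFS truly effective; OS and response null. A false claim is made if OS is rejected, or if the gate opens and response is rejected. When OS is not rejected, the gate can open only through PFS. Duration adds nothing here, because it is reached only after response has been (falsely) rejected.

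**Cumulative error through the final OS test, independence.** 0.025 + 0.975 × (PFS power) × 0.05:

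- power 0.80: 0.025 + 0.0390 = 6.4% (6.3% with the reproduced 78.3%)
- power 0.90: 0.025 + 0.0439 = 6.9%
- power near 1: 0.025 + 0.04875 = 7.4%
- bound for any correlation: 0.025 + 0.05 = 7.5%

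**Correlated statistics.** Trivariate normal simulation, 8 million draws, OS tested once, the same correlation for every pair. The fourth column counts only false claims in favour of lenalidomide, for which the implied limit is 0.0125 + 0.0125 = 2.5%. The last column tests the sequence at 0.025 after a single win.

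| Correlation | 80% power | 90% power | 80%, favouring lenalidomide only | 80%, sequence at 0.025 |
|---|---|---|---|---|
| 0 | 6.40% | 6.88% | 3.23% | 4.45% |
| 0.3 | 6.08% | 6.57% | 3.49% | 4.25% |
| 0.5 | 5.55% | 6.00% | 3.45% | 3.92% |
| 0.6 | 5.22% | 5.63% | 3.37% | 3.74% |
| 0.7 | 4.82% | 5.22% | 3.22% | 3.51% |
| 0.8 | 4.43% | 4.72% | 3.05% | 3.30% |

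Modelling both OS looks at correlation 0.6 and 80% power gives 5.3% instead of 5.2%.

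**PFS step alone.** The SAP's boundary table is redacted, so I assume Lan-DeMets spending of O'Brien-Fleming type: two-sided 0.0025 is spent on OS at 60% information. Under independence the error is 0.0025 + 0.9975 × power × 0.05 = 4.2% (power 0.80), 4.7% (0.90) and 5.2% (near 1). Almost all of the excess therefore builds up later, through the final OS test.

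**Where there is no excess.** With all three null, every false claim needs a false co-primary win, so the error is at most 0.025 + 0.025 (1 − 0.975² = 4.9% under independence). With both co-primaries effective and response tested once, the error is at most 0.05.

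**After the fix.** Under independence, 0.025 + 0.975 × power × 0.025 = 4.4% at power 0.80 (0.0445) and 4.9% near 1. For any correlation it is at most 5%: 0.025 + 0.025 when one co-primary and response are null, 0.05 when only response is null, and 0.025 + 0.025 when all three are null.

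**The case against.** The strongest objection concerns the benchmark. SAP 11 and 6.1 apply the adjustment to the primary analyses, and nothing visible promises 5% over primaries and secondaries together. That is correct, and the 5% here is an inference. But a gated fixed sequence has little purpose unless the claims behind it are meant to be protected.

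Second, independence is close to a worst case. Deaths count in both PFS and OS, and PFS and response rest on the same adjudicated response data. This stands: 6.4% should be read as the upper part of a range, and with two-sided counting at 80% power the excess is gone at a correlation of 0.7. It does not disappear when only errors favouring lenalidomide are counted; those stay above 2.5% at every correlation tried.

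Third, the setting is narrow: one co-primary works, while the other and response do not. This is true.

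Fourth, the current protocol has moved on. OS is the only primary endpoint (Synopsis; section 7.1), the visible secondary endpoints are safety and PFS2 (7.2), response improvement is only cross-tabulated (16.3.3), and the Response Adjudication Committee is no longer used (Synopsis). PFS2 is not in the SAP sequence at all. This limits the point to any use of the SAP's co-primary scheme for secondary claims, and is a reason to settle the sequence's status.

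Fifth, part of SAP 14.2, on control of alpha, is redacted, so a rule for the secondaries could be hidden there. It would then conflict with the explicit 0.05 in 11.2.1 and 11.2.2, which would still need correcting.

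**Conclusion.** The concern holds. The SAP opens the secondary sequence on either co-primary win and tests it at twice the level that a single win releases. With PFS effective and OS and response null, cumulative error is 6.4% at 80% PFS power under independence, about 5.2% at an assumed common correlation of 0.6, and never above 7.5%. The figures rest on the implied 5% benchmark and on assumed correlations; at 80% power and a correlation of 0.7 or more the two-sided rate is below 5%. The PFS and OS claims are not affected. The correction should be made wherever this sequence is still used to support claims.

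**What to change.** In SAP 11, 11.2.1 and 11.2.2, state two rules:

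1. The sequence is tested at two-sided 0.025 if exactly one co-primary is significant, and at two-sided 0.05 only if both are.
2. Response and duration data are frozen at the cut-off of the first co-primary win. A later second win re-reads the same p-values against 0.05 and does not retest updated data.

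The second rule is needed for the 5% bound. If response were tested at 0.025 first and again on updated data at 0.05 after a later OS win, error with both co-primaries effective could reach 5.6% to 6.1% (assumed correlation between the two response tests 0.9 to 0.8).

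Separately, state whether the sequence keeps confirmatory status now that OS is the only primary endpoint in the protocol.

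The cost is about three sentences and some secondary power after a single win. A test with 80% power at 0.05 has 71% at 0.025 (1.960 + 0.842 − 2.241 = 0.560), and one with 90% has 84% (1.960 + 1.282 − 2.241 = 1.000). Response data that mature after the first win would be descriptive only.
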